## **Safety Analyses**

All participants will be included in the safety analyses.

The circumstances of all reportable adverse events (AE) from the following list will be summarized and tabulated by treatment group:

- Severe hypoglycemic events
- Hyperglycemic crisis (DKA/HHS) events
- CGM-measured hypoglycemia events <54 mg/dL (15 or more minutes)
- Other serious adverse events (SAE)
- Unanticipated adverse device effects (UADE)
- Adverse device effects (ADE)
- Other adverse events

Statistical analyses to compare rates of severe hypoglycemia events between treatment arms will only be performed if there are at least 5 total events after randomization in both groups. If so, the numbers will be compared between the two treatment periods using a robust Poisson regression. The amount of follow up will be included as an offset covariate to compare the rates.

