**Table 1. Study Summary**

Project Title	Automated Insulin Delivery for Inpatients with Dysglycemia (AIDING) Randomized Controlled Trial
Précis	This randomized controlled trial will test the efficacy and safety of automated insulin delivery (AID) in hospitalized patients with diabetes (type 1 or type 2) requiring insulin therapy who are admitted to general medical/surgical floors. Participants will be randomized to AID + remote CGM (intervention) or multiple daily insulin injections (MDI) + CGM (control group). Participants will be followed for a total of 10 days or until hospital discharge (if less than 10 days).
Study Design	Open label, multicenter, randomized (1:1), parallel-group, clinical trial.
Objectives	
Primary objective: To test the efficacy and safety of AID versus standard of care therapy in the inpatient setting.
 
Secondary objectives: To determine differences in CGM derived metrics between AID and standard of care therapy in the hospital and explore differences in treatment effect according to individual characteristics.

Research Intervention	The Omnipod 5 system, consists of a disposable insulin infusion pump (or “pod”), a built-in model predictive control (MPC) insulin dosing algorithm, and a remote smartphone interface (Controller), that interact with a Dexcom G7 continuous glucose monitor (CGM) to automatically control insulin delivery based upon real-time glucose values. The Controller component also enables remote interaction with the system, including glucose monitoring as well as insulin dosing management and adjustments. The control group will wear a Dexcom G7 CGM.
Treatment Groups	Participants will be randomized to AID + CGM or to MDI + CGM for up to 10 days or until hospital discharge.
Population	
Key Inclusion Criteria:
 
Any person <math>\geq 18</math> years of age with diabetes mellitus (except cystic fibrosis- and pregnancy-related) admitted to general (non-ICU)

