**Table 2. Sample size estimates**

Treatment Effect			
5%	10%	15%	20%
N=504	N=126	N=56	N=32

It should be noted, sample sizes are typically increased by 10-15% to account for potential dropout.

An N=100 gives a power of 99% to detect a difference of 15% between groups at a standard deviation of 16% (AIDING pilot) or 17.3% (prior trials) and  $\alpha=0.05$ . An N=56 gives a power of 90% to detect a difference of 15%. To include at least 20 participants in subgroups of interest (T1D, renal disease, and steroid exposure) for the exploratory analysis and at least 100 participants with  $\geq 48$  hours of device use for the efficacy and safety analysis, we will enroll a total of 120 participants with sufficient CGM data.

**CGM Data Sufficiency Definition:** A minimum of 70% of data per patient day and a minimum of 24 hours in sensor duration will serve as the thresholds for inclusion in the per-protocol analysis (Spanakis et al 2023).

**Table 3** shows the minimum detectable differences for a range of sample sizes.

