#### Statistical Hypotheses

This trial has a primary outcome of percent time in range (% TIR), defined as CGM-measured glucose between the range of 70-180 mg/dL. This will be tested using a two-sided test of superiority. The two groups being compared are those using the Dexcom G7 in conjunction with the Omnipod 5 (automated insulin delivery) and those receiving the standard of care (multiple daily injections of insulin with CGM for detection of hypoglycemia). Participants will be followed for a minimum of 48 hours and a maximum of 10 days. The study will be conducted in an in-patient hospital setting (non-ICU) across three sites and will include any participant with diagnosed diabetes (e.g., T1D, T2D) requiring insulin treatment.

Hypotheses:

- a. *Null Hypothesis:* There is no difference in % TIR between the Standard of Care (control) and AID (experimental) groups.
- b. *Alternative Hypothesis:* there is a difference in % TIR between the Control and Experimental groups.

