**Description of Statistical Methods**

**General Approach**

The intent-to-treat (ITT) approach will be used with each participant analyzed in the group to which they were randomized regardless of treatment received. A sensitivity (per-protocol) analysis

will also be conducted for participants with >24 and 48 hours of data. This analysis will assess the robustness of the primary findings to protocol adherence and sufficient exposure to AID.

All p-values, unless otherwise noted, will be two-sided. Percent time below 70 mg/dL and time below 54 mg/dL will initially be tested as non-inferior; if the alternative hypothesis is not rejected, these metrics will then be tested for superiority. Time below 54 mg/dL will be tested separately (primary safety endpoint).

It is expected % TIR will be normally distributed and can be assessed with a standard linear regression approach. If residuals are skewed, a nonparametric or robust regression approach will be used. Other outcomes not normally distributed will also be assessed using a nonparametric or robust regression approach. The outcomes most likely to be skewed from past experience are the % time below 70 mg/dL and 54 mg/dL.

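### The severe-hypoglycemia rate test has a trigger with two readings and names robust Poisson regression without a rule for an arm with no events, where that model gives a false p-value near zero

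*SAP*

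**What the plan says.** The SAP, Safety Analyses, introduces "Statistical analyses to compare rates of severe hypoglycemia events between treatment arms" and makes them conditional: they "will only be performed if there are at least 5 total events after randomization in both groups". If the condition is met, "the numbers will be compared between the two treatment periods using a robust Poisson regression". Follow-up enters as an offset: "The amount of follow up will be included as an offset covariate to compare the rates".

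The text does not say whether five is the pooled count or the count in each arm. It does not define robust, and it gives no method for an arm without events.

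Other parts of the SAP bear on this:
- Table 1 describes the design as "Open label, multicenter, randomized (1:1), parallel-group, clinical trial".
- On size, the text after Table 2 says "we will enroll a total of 120 participants with sufficient CGM data".
- On duration, Statistical Hypotheses says "Participants will be followed for a minimum of 48 hours and a maximum of 10 days".
- General Approach says "All p-values, unless otherwise noted, will be two-sided".
- No expected rate of severe hypoglycemia is stated.

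**The concern.** This is the only between-arm rate test that the SAP plans for severe hypoglycemia events. Two things about it are not fixed well.

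First, the condition that decides whether the test is run has two readings. In an open-label trial that choice should not be left until the counts are known.

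Second, under the more natural (pooled) reading, the plan sends as few as five events to a model that cannot estimate a rate ratio when one arm has none. With a sandwich variance the failure does not show in the standard error. The output can look like near-certain harm or benefit.

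A smaller matter is that the model sentence compares periods, although each participant in a parallel-group trial receives one assigned treatment.

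**Working it through.** The five-event trigger is a rule, not a derived figure, so the plan has no number of its own to reproduce here.

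**Inputs.** From the SAP: trigger of 5 events, robust Poisson regression with a follow-up offset, 1:1 parallel groups, two-sided tests, 120 participants. Assumed, because the SAP gives no value: 60 per arm, equal follow-up, one event per affected participant unless stated, robust meaning a sandwich (HC0) variance, and the expected event totals and rate ratios used below.

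**1. The two readings of the trigger.** With Poisson counts and 5 events expected in all:
- Pooled: P(total ≥ 5) = 0.56.
- Each arm, rate ratio 1 (mean 2.5 per arm): P(≥ 5 in both) = 0.012.
- Each arm, rate ratio 0.25 (means 1 and 4): 0.001.

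With 10 expected, the figures are 0.97, 0.31 and 0.047.

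Under the each-arm reading 9 v 0 would go untested, although its exact two-sided p is 2 × 0.5⁹ = 0.004. So would 14 v 4 (exact p = 0.031).

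**2. How often an arm is empty under the pooled reading.** Given exactly 5 independent events and rate ratio r, let q = r/(1 + r). Then P(empty arm) = q⁵ + (1 − q)⁵.
- r = 1: 2 × 0.5⁵ = 0.0625
- r = 0.5: 0.136
- r = 0.25: 0.2⁵ + 0.8⁵ = 0.328

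Over all totals that meet the trigger, with 5 events expected, the figures are lower: 0.032 at r = 1 and 0.244 at r = 0.25.

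**3. What the model returns at 5 v 0.** The maximum-likelihood log rate ratio is infinite. Software stops at about 21.4 in absolute value, at a point set by its tolerance, and reports convergence.

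The HC0 variance of the log rate in an arm is Σ(y − μ)²/(Σμ)².
- Arm with 5 events among 60: 1/5 − 1/60 = 0.1833.
- Empty arm: 60μ²/(60μ)² = 1/60, however small the fitted μ becomes.
- Sum: 0.2, so SE = √0.2 = 0.447.

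When the empty arm is coded as the reference, rounding loses the 1/60 term and the software prints √0.1833 = 0.43. Either way z is about 48 to 50 and p is 0 to machine precision.

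The model-based SE for the same data is about 11,949 (p = 0.999). The exact conditional test gives 2 × 0.5⁵ = 0.0625.

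**4. Where the fault stops.** At 4 v 1, the log rate ratio is ln 4 = 1.386. The HC0 variance is (1/4 − 1/60) + (1 − 1/60) = 1.217, so SE = 1.103, z = 1.26 and p = 0.21 (exact p 0.375). The model has a finite estimate and an ordinary standard error once both arms have an event.

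**5. Repeat events.** Suppose six events fall in one participant and none in the other arm. The HC0 variance is (1 − 1/60) + 1/60 = 1, so SE = 1. The log rate ratio is about 22.4 and p is again about 0. The exact conditional test on event counts gives 2 × 0.5⁶ = 0.031 from one person. Comparing participants with any event, 1/60 v 0/60, Fisher's exact p is 1. The fallback must therefore work at the participant level.

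**The case against.** Several points on the other side stand.

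- **Hypoglycemia is tested elsewhere.** A reader might infer that this is the plan's only formal comparison of the main harm of insulin. It is not. Time below 54 mg/dL is the primary safety endpoint, tested for non-inferiority and then superiority, and time below 70 mg/dL is in the hierarchy.
- **The pooled reading is the natural one.** The word total would have little purpose if five were needed in each arm. A reader might infer that the plan suppresses one-sided harm. That follows only from the less natural reading, and no stated event rate suggests that counts such as 9 or 14 are likely.
- **The two faults exclude each other.** Under the each-arm reading an empty arm never reaches the model. Under the pooled reading 9 v 0 is tested. Only one of them can occur, but neither reading is free of a fault.
- **Events are not hidden.** The same section tabulates reportable events by treatment group without any trigger, so a 5 v 0 split would be seen.
- **The breakdown is narrow and partly visible.** It needs an empty arm, and a log rate ratio above 20 should alert an analyst. With independent events and equal follow-up, the decision at 5% changes only at exactly 5 v 0, since 6 v 0 already has exact p = 0.031. The estimate and interval are meaningless at every empty-arm split, however, and repeat events widen the range in which the p-value misleads.
- **Periods is a slip.** The preceding sentence speaks of arms, so the intended comparison is clear.

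**Conclusion.** The point holds for this one conditional safety comparison. The trigger should have one reading. Under its natural reading, the named model lacks a rule for a foreseeable outcome and can then report p near 0 where the exact p is 0.0625. Given exactly five independent events, that outcome has probability 6.25% with no true difference and about 33% at a true rate ratio of 0.25.

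These figures assume equal follow-up and a sandwich variance; the standard errors also assume 60 per arm. The SAP gives no event rate, so the chance of reaching the trigger at all is unknown.

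The documents do not support a claim that the trial's overall hypoglycemia conclusion is at risk, or that harm would go unreported. Efficacy, sample size and the tests of time below 54 and 70 mg/dL are untouched.

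**What to change.** In the SAP, Safety Analyses:

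1. State the trigger as at least 5 events in the two groups combined.
2. Replace treatment periods with treatment groups.
3. Say that robust means a sandwich variance, if that is intended, and keep this model when both arms have at least one event.
4. When an arm has no events, replace the model with a pre-specified exact method that allows for repeat events. Examples are an exact test of participants with any event against none, or a permutation test of participant event rates, with an exact confidence interval. Because follow-up varies between participants, the version based on rates uses it and the any-event version does not. Choose one in advance.
5. In all cases report events, participants with an event, and rates per patient-day by arm. Event tabulation by group is already planned, so this mainly adds the participant counts and rates.

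**Cost.** A wording change and a few lines of code, with no new data. At exactly five events with equal follow-up, an exact test cannot reach p < 0.05. The conditional test gives 0.0625 at best. Fisher's test for five affected participants against none, 60 per arm, gives 2 × (60·59·58·57·56)/(120·119·118·117·116) = 0.057. At the threshold the comparison is therefore mainly descriptive, and the SAP should say so.

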## **Device Issues**

Device issues and complaints will be tabulated and reported for each group.

### **Protocol Adherence**

The following tabulations will be done for each treatment group:

- Number of deviations per participant and the percentage of participants with each deviation.
- Protocol deviations by severity.
- Flow chart accounting for participants.
- Descriptions for participants who withdrew.
- Number of days in the trial for each participant and reason for ending.

### **Baseline Descriptive Statistics**

Baseline descriptive statistics will be tabulated for each treatment group with appropriate summary statistics used for the distribution. The characteristics used will include:

- Reason for hospitalization
- Age
- Sex
- Race/ethnicity
- Insurance status
- Education
- Income
- Diabetes duration
- Diabetes type
- BMI
- Glucose at randomization
- Diabetes treatment
- HbA1c
- Relevant labs (HbA1c, creatinine, eGFR)
- Comorbidities
- Corticosteroid use during the trial

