## Version History

Version	Principal Investigator	Statistician	Effective Date	Protocol Version
1.2	[name]	[name]	11/07/2025	1.8

Changes and Clarifications:

Clarifications regarding intent-to-treat (ITT) and per-protocol (PP) analyses (sensitivity analysis). The primary analysis will follow the intent-to-treat (ITT) principle, including all randomized participants. The per-protocol (PP) sensitivity analysis will be limited to participants meeting data sufficiency criteria ( $\geq 70\%$  of data per patient day and  $\geq 24-48$  hours of sensor wear; Spanakis et al., 2023). Clarification of reference related to power calculations and standard deviations based on prior studies and the pilot trial. Expanded baseline descriptive variables to include education, income, and corticosteroid use, as well as planned inclusion of corticosteroid exposure in subgroup exploratory analysis.

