## **Analysis Cohorts**

### **Safety Analyses**

All safety outcomes will be reported for all participants throughout the study.

Any baseline factors found to be imbalanced between treatment groups will be added as covariates to the analysis.

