### **Subgroup Description**

Outcomes will be assessed for subgroup characteristics by treatment group if they are found to be statistically significant. The baseline factors will include:

- Baseline HbA1c
- Baseline glucose
- Age
- Sex
- Race/ethnicity
- Insurance status
- Diabetes type
- Kidney disease
- Corticosteroid use
- Pre-study insulin use

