### **Exploratory Analyses**

As a subgroup analysis, differences in treatment effect will be examined. Including comparisons of treatment across BMI ranges, sex, HbA1c, steroid use, and renal function. It is expected most cases (~80%) will be T2D cases. To explore differences in treatment effect among participants with T1D we will enroll a minimum of 20 participants with T1D.

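### The only time window the SAP gives for corticosteroid use falls after randomisation, yet the variable is filed as baseline and used for an exploratory subgroup

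*SAP*

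**What the plan says.** Under Baseline Descriptive Statistics the SAP states: "Baseline descriptive statistics will be tabulated for each treatment group with appropriate summary statistics used for the distribution". The last item in that list is "Corticosteroid use during the trial".

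Subgroup Description introduces its list with "The baseline factors will include" and includes corticosteroid use with no time window. Exploratory Analyses plans to examine differences in treatment effect, "Including comparisons of treatment across BMI ranges, sex, HbA1c, steroid use, and renal function". Section II (Sample Size Calculation and Power Analysis) gives this as one reason for enrolling 120: "To include at least 20 participants in subgroups of interest (T1D, renal disease, and steroid exposure) for the exploratory analysis". The Version History adds both roles in one sentence, expanding the baseline variables to include "corticosteroid use, as well as planned inclusion of corticosteroid exposure in subgroup exploratory analysis".

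Under Analysis Cohorts, in the paragraph headed Safety Analyses, there is also a general rule: "Any baseline factors found to be imbalanced between treatment groups will be added as covariates to the analysis".

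**The concern.** A baseline characteristic has to be fixed by the time of randomisation. Steroid use during the trial is known only afterwards and can depend on clinical course, length of stay and care given in an open-label setting. Randomisation balances the arms within groups formed from baseline variables. It gives no such protection within groups formed from later events.

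Two things are at stake. The first is the interpretation of the exploratory AID-versus-control contrast among steroid-exposed participants. The second is any adjustment triggered by imbalance. A post-randomisation variable labelled as baseline would be called in as a covariate exactly when the arms diverge on it, which is when adjusting for it may do harm.

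**Working it through.** **1. The places side by side**

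| SAP section | Role of steroid use | Window given |
|---|---|---|
| Baseline Descriptive Statistics | baseline characteristic | during the trial |
| Subgroup Description | baseline factor for subgroups | none |
| Exploratory Analyses | treatment-effect comparison | none |
| Section II, text after Tables 2 and 3 | subgroup with a target of at least 20 | none |
| Version History | baseline variable and subgroup, one sentence | none |

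The SAP does anchor other variables in time. Glucose in the baseline table is tied to randomisation. In the subgroup list, HbA1c and glucose are marked as baseline and insulin use as pre-study. The steroid item has no such anchor, and its one stated window lies after randomisation. There are two readings. Either the table's window carries over and the subgroup is post-randomisation, or the subgroup means use at baseline and the table contradicts it. Both need correcting.

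**2. The plan's figure for a group of 20**

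The definition itself has no stated figure. The only figure tied to a subgroup of 20 is the power in Table 4, which the text gives for type 1 diabetes. The inputs are 10 per arm, a difference of 20 points, two-sided alpha 0.05 and SD 16 or 17.3. Power = Φ(difference/SE − 1.96), with SE = SD × √(2/10).

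- SD 16: SE = 7.16; 20/7.16 − 1.96 = 0.835; power 0.798 (Table 4: 0.798).
- SD 17.3: SE = 7.74; 20/7.74 − 1.96 = 0.625; power 0.734 (Table 4: 0.734).

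Both reproduce. The standard error of about 7 points is the yardstick for step 4.

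**3. Does membership depend on follow-up?**

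Statistical Hypotheses sets follow-up at 48 hours to 10 days. Let h be an assumed constant daily probability of starting steroids (the SAP gives none). Then P(exposed by day d) = 1 − (1 − h)^d.

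| h | 2 days | 10 days |
|---|---|---|
| 1% | 2% | 10% |
| 3% | 6% | 26% |
| 5% | 10% | 40% |
| 10% | 19% | 65% |

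This counts new starts only. If 20% of participants were already on steroids at entry (also assumed), h = 3% gives 0.20 + 0.80 × 0.059 = 25% at 2 days and 0.20 + 0.80 × 0.263 = 41% at 10 days. The ratio falls from about 4.5 to about 1.7. Membership depends on follow-up, but how strongly is not known from the SAP.

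**4. How large could the bias be?**

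Simulation of 2,000,000 participants allocated 1:1, with a true effect of 15 points in everyone and SD 16. An unmeasured severity score correlates −0.3 or −0.5 with time in range. The log-odds of steroid use are −1.4 + 0.8 × severity + g × arm.

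| Arm effect g | Exposed, control v AID | Effect among exposed (correlation −0.3; −0.5) |
|---|---|---|
| 0 | 22% v 22% | 15.1; 15.1 |
| −0.5 | 22% v 15–16% | 14.8; 14.6 |
| −1.0 | 22% v 10% | 14.6; 14.1 |

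With no arm effect on steroid use, the contrast stays at about 15. With exposure of 22% v 10%, it moves by 0.4 to 0.9 points. The upper end is 0.9/7.16, about an eighth of the standard error with 10 per arm.

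**5. Can it reach the primary analysis?**

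The section on analysis of % TIR names the covariates: age, insulin treatment, baseline HbA1c, diabetes type and site. Steroid use is not among them. It could enter only if the imbalance rule is read as adding to that list, and if the table's label makes steroid use a baseline factor.

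**The case against.** The window after randomisation appears only in a descriptive table. The subgroup section calls its factors baseline and sets steroid use beside items that are plainly pre-randomisation, so on its face it may mean steroid use at entry. The Version History puts the two uses in one sentence but does not say that they share a window. This stands. A reader might infer that the steroid analysis is certain to condition on a post-randomisation variable. The SAP supports only the alternative set out above: it does so, or it contradicts itself.

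A reader might also infer that the steroid subgroup would be largely a long-stay subgroup. That does not follow. It ignores participants already on steroids at entry, whom the plan appears to expect, since Table 1's exclusion for stress hyperglycaemia leaves out steroid-related cases. It also needs a distribution of stay that the SAP does not give. Dependence on length of stay does not by itself bias the arm contrast.

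Nothing in the SAP says that assignment alters steroid prescribing, and the arms differ in insulin delivery. This also stands. The open-label design and unequal follow-up mean only that an influence cannot be excluded. Finally, the subgroup is exploratory, and no test in the hierarchy rests on it.

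**Conclusion.** The point holds as a defect of definition. The baseline table carries a post-randomisation item, and its window is the only one the SAP gives for a variable also used as a subgroup factor and a recruitment target. The consequence is limited to the exploratory steroid analysis. Bias there requires assignment to affect steroid use or time at risk. Under the assumed settings it is modest: 0.4 to 0.9 points on a 15-point effect, well inside a standard error of about 7.

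A reader might conclude that the main comparison is biased. The SAP does not support that: the named primary covariates omit steroids, and the imbalance rule sits under a safety heading. Because that rule speaks only of the analysis, without saying which, the route is unclear rather than closed.

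The daily start probabilities, the 20% already on steroids, the severity correlations and the arm difference in exposure are all assumptions. The conflict between the sections depends on none of them. This is a minor point that should still be corrected before unblinded analysis, so that the steroid definition is not chosen after the data are seen.

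**What to change.** Define the baseline row, the subgroup factor, the treatment-effect comparison and the 20-participant target by one variable: corticosteroid treatment active at randomisation, or in a stated window before it. The length of any look-back is the sponsor's choice, but it needs to be written down. Report steroid use during the trial by arm, labelled as a post-randomisation descriptive. State that it is not a baseline factor for the imbalance-covariate rule.

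The cost is mainly SAP wording, assuming that steroid treatment at randomisation is already recorded, which the SAP does not say. The downside is that participants who start steroids only after randomisation would no longer count as exposed. Their number is unknown, so the target of at least 20 should be checked against the new definition.
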